6. HYPOTHESES AND OBJECTIVES

6.1 Hypotheses

A dynamic choice prevention model that includes a patient-entered CAB-LA delivery option will have higher levels of biomedical prevention coverage (assessed over 48 weeks following re-consent for the CAB-LA extension study) compared to the standard of care.

This hypothesis will be tested by comparing covered time between the intervention and control arms in the 3 ongoing randomized trials during the extension phase.

The secondary hypothesis: Addition of patient-centered CAB-LA into an ongoing dynamic choice prevention will improve biomedical prevention coverage (compared to dynamic choice prevention without CAB-LA).

These hypotheses will be tested by comparing covered time during the extension with the CAB-LA option to covered time prior to the extension among intervention arm participants.

We expect that incorporating the option of CAB-LA with patient-centered delivery for persons who self-identify at risk for HIV living in rural Uganda and Kenya will increase overall biomedical covered prevention time compared to the standard of care. In a population that has been offered -- and some of whom have taken up -- oral PrEP and PEP, we also expect to learn characteristics of who is most interested in CAB-LA, how our patient-centered CAB-LA delivery models work in different settings, and the cost of the delivery models in different settings.

6.2 Objectives

Primary Objective: To compare biomedical prevention coverage achieved using a Dynamic prevention model that includes a patient-centered CAB-LA delivery intervention to biomedical prevention coverage under the standard of care over 48 weeks.

Secondary Objectives: To determine the reach, effectiveness, adoption, implementation and maintenance of a patient-centered CAB-LA program embedded in 3 ongoing trials in the setting of antenatal clinic, outpatient clinic, and community.

[figure not shown]
Tertiary Objectives: To evaluate change in knowledge, awareness and acceptability/satisfaction at the staff and provider level with CAB-LA before and after provider and staff training and education in CAB-LA with patient-centered delivery model.

7. INTERVENTION

7.1 Study Design and Schema

Study Design: This proposal is an **extension of 3 ongoing randomized trials comparing a patient-centered “Dynamic Choice” implementation strategy for delivering biomedical prevention options compared to standard of care** (Figure 1). Each trial is enrolling persons 15 years of age and older who are HIV uninfected and at risk of acquiring HIV. The Dynamic Choice Prevention intervention allows choice of PEP/PrEP, refill schedule, service delivery location (e.g. clinic, community, home), and HIV testing (self or staff). Persons can move from PEP to PrEP as they prefer.

Figure 1. Dynamic Choice Implementation Strategy.

Intervention: In the extension phase, participants will remain in their initial randomization arm. For persons in the intervention arm, CAB-LA will be integrated into the dynamic choice delivery model as an additional biomedical prevention option in a patient-centered delivery model based on the precede framework.

7.2 Dynamic Choice Delivery Model

The Dynamic Choice Delivery Model includes integrated PrEP and PEP services at outpatient clinics, antenatal clinics, and via VHT workers in community households. The procedures for each trial include PrEP/PEP counseling and services, choice of service location, HIV testing options, option for longer PrEP refills, provision of a clinical officer’s or nurse’s mobile telephone number for immediate PEP starts any day of the week, assessment of PrEP/PEP barriers and personalized actions, psychologic supports for traumatic experiences, and offer of concurrent, additional health or prevention related services. For participants that chose CAB-LA as the biomedical prevention option, the patient-centered delivery model (Table 3) will be implemented. The standard of care differs according to country but does not routinely offer PEP or PrEP to clients seeking services, does not offer choice of service location, HIV testing option or access to medical provider mobile phone number. Clients are required to return after one month for a refill for PrEP, whereas in our model, there is an option from the start for 3 month medication supply.

Table 3. Patient-Centered Delivery Model.

Intervention	Population and frequency	Purpose
Education, case studies and discussion on concept of dynamic prevention and on the profile of each prevention option product	Health center leadership and staff, provider, participants; initial and ongoing	Predisposing
Integration into antenatal, OPD clinics, IPV/GBV support services, travel packs, 24 hour hotline for participants For oral PrEP/PEP only- HIV testing choice (self or staff) and home or clinic delivery	Participants; ongoing	Enabling
Provider text/check-in to participant one week after starting new option, data on biomedical prevention covered time (reinforcing)	Participants and staff; ongoing data feedback	Reinforcing

7.3 Measurement

Outcomes: The primary outcome for the extension is the proportion of time covered by a biomedical prevention option during the 48 week follow-up period of the CAB-LA Extension; follow-up time will be censored at HIV diagnosis, death, or withdrawal. Biomedical covered time is defined as the proportion of follow-up time that each participant is covered by either PrEP (TDF/3TC or CAB-LA) or PEP. For TDF/3TC, covered time is defined using self-reported use; in a subset of participants who report PrEP use we will measure tenofovir drug levels using small hair samples to allow for calibration of self-reported measures. For CAB-LA, coverage begins 3 days after initial injection continues 2 months + 7 days after last injection. For PEP, covered time is defined using self-reported use; in a subset of participants who report PEP use we will measure drug levels using hair samples to allow for calibration of self-reported measures. A secondary outcome for the extension is “at-risk covered time”, defined as the proportion of time that a participant reports being at risk of HIV infection during which they are covered by a biomedical prevention option. Incident HIV infections, defined by a prespecified testing algorithm, will be an additional secondary outcome.

Secondary outcomes of reach, effectiveness, adoption, implementation and maintenance will be evaluated using a mixed methods approach that includes surveys of participants, and health center providers and staff. Tertiary outcomes of knowledge, awareness and acceptability/satisfaction at the staff and provider level will be measured by surveys at the baseline, midpoint and end of the study. Measurement details are delineated in Table 4 .

7.3.1 Behavioral Measures

In addition to these surveys, trained staff will conduct in depth interviews (IDI) to provide insights into the intervention implementation and attitudes of participants and staff. These qualitative in-depth interviews will be conducted among purposively-selected samples of study participants and providers, to ascertain the perceptions of and experiences with CAB-LA use and delivery. Participants who are clients will be asked about 1) Experiences with counseling, method/service preferences and decision-making to go on CAB-LA; 2) Method/services satisfaction, barriers and facilitators to uptake and maintenance, and social networks and support as a facilitator or hindrance; and 3) Recommendations to improve CAB-LA Delivery. Health

care providers engaged in CAB-LA service delivery will be asked about their 1) Professional identity and motivation, as a potential factor influencing implementation; 2) First impressions and knowledge of CAB-LA; 3) Clinical training experiences relevant to CAB-LA provision; 4) Experiences with and acceptability of individual elements of CAB-LA; and 5) Recommendations for improving CAB-LA delivery.

For all research activities related to qualitative evaluation of SEARCH SAPPHIRE, written informed consent will be obtained from all selected for recruitment to the study.

Qualitative IDIs for CAB-LA will be conducted between 2-6 months from enrolment. The specific data collection activities to be conducted during the phase are listed below. For Seroconverts, IDIs are will continue until the maximum number of participants is reached or the study intervention ends, whichever comes first.

- i. CAB-LA Patient IDI cohort: We will systematically select $\sim n=30$ patients per each region (South West Uganda and Kenya) (total $40 < \sim n < 72$), with samples within region to be balanced by original trials (Out- patient, ANC/PNC, VHT); further balance to be observed by gender and community, proportional to overall intervention enrolment.
- ii. CAB-LA Provider IDI cohort: We will select a sample of care providers who administer CAB-LA from the CAB-LA trial health facilities or who inform the community about that option (VHTs / CHVs per each region. I.e. $n=2-3$ OPD providers, $n=2-3$ ANC/PNC providers, $n=1-2$ VHTs per region (total $8 < \sim n < 12$ providers per region).
- iii. Seroconverts Patient IDI cohort: We aim to interview all participants in the intervention arm who received a diagnosis of HIV during the course of the DCP study and who are willing to be interviewed, up to a total of 36 per country.

For this study, IDIs will be recorded using the TASCAM DR-05 digital recorder. This digital recording device was selected for use in this study because it has a high quality microphone that captures high quality sound even in settings with a lot of ambient background noise.

For this study, the interviews will be conducted in the participant's preferred language. The Qualitative study team will then transcribe and translate the audio recorded data into English for analysis within 14 days of the interview. Staff will use either Express Scribe or VideoLAN Client (VLC) software for this process. QRCs/QRAs will share responsibility for coding all transcriptions of recorded IDIs. Coding will be conducted in Dedoose using a codebook developed iteratively by the team. Analysis will follow a modified framework analysis of key code excerpts exported from Dedoose after coding.

7.3.2 Costing Evaluations

Costing of CAB-LA implementation will be conducted in each region and location type (Antenatal Clinic, Outpatient Department, Community) at Baseline/Screening and at two injection visits during follow-up. Costing exercises will employ an activity-based approach and include site visits and employ rigorous costing methods using standardized micro-costing tools.

We will also conduct time-and-motion activities using self-administered tools with on-site staff to estimate the amount of time spent implementing CAB-LA. We will interview study staff to identify resources used to implement the intervention and estimate time spent providing oversight and management of implementation activities.

Implementation Research Design: The secondary objective of the extension is an implementation evaluation of the intervention focused on the initial implementation of patient-centered CAB-LA using the RE-AIM framework. The domains of interest and key outcomes are summarized in the table below. Throughout, study weeks are used to refer to weeks in CAB-LA extension (eg, “week 0” is date of re-consent for the CAB-LA extension, “week 48” is 48 weeks after re-consent for the CAB-LA extension).

Table 4. RE-AIM Evaluation Framework.

Domain /Outcome	Definition	Measurement	Timing
Reach (Participant level)	Proportion of eligible participants who initiate CAB-LA weeks 0-48. Characteristics (including prior PrEP and PEP use) and attitudes (knowledge, acceptability and feasibility) of participants using CAB-LA	Demographics, CAB-LA dispensing logs Knowledge, Acceptability and Feasibility (Survey and IDI). Evaluation includes focus on equitable access by gender, education and SES.	CAB LA dispensing throughout follow-up Surveys and IDI: Week 0, 24 and week 48
Effectiveness (Participant level)	Impact of adding CAB-LA to Dynamic choice prevention on biomedical covered time (comparison of follow-up during the CAB-LA extension vs. follow-up time in Phase A trials prior to CAB-LA extension).	CAB-LA dispensing logs, PrEP and PEP use as defined for primary endpoint in extension.	Throughout follow-up
Adoption (Provider and staff level in different settings)	% of staff and providers invited that participate in the interventions, where participation is defined as i) participation in CAB-LA trainings; and ii) offering CAB-LA to participants. We will further assess the characteristics of participant vs. non-participant staff.	Training attendance rosters; CAB-LA dispensing logs	Throughout follow-up
Implementation (Provider and systems level)	Fidelity : Proportion of providers offering CAB-LA on appropriate schedule, appropriate provision of oral bridging Costing : Incremental cost of adding CAB-LA to dynamic choice prevention Adaptations : Type, timing and reasons they were made	CAB-LA and oral bridging dispensing logs Time in motion and program costing Adaptation logs	Throughout follow-up
Maintenance (adapted from standard RE-AIM to accommodate shorter follow-up) (Participant level)	Persistence on CAB-LA among participants who initiate CAB-LA Reasons for discontinuation of biomedical prevention or switching to other biomedical prevention option	CAB-LA dispensing logs Participant survey on reasons for discontinuation and switching	Throughout follow up

As a tertiary objective, we will also assess provider and staff Knowledge, Acceptability and Awareness via provider and staff surveys (Likert scales) and IDI at weeks 0, 24, and 48.

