This extension describes a 48-week extension of 3 ongoing randomized trials in SEARCH Phase A studying a patient-centered “Dynamic Choice Prevention” (DCP) implementation strategy for delivering existing evidence-based biomedical prevention interventions vs. standard of care (SOC). The Dynamic prevention model offers participants choices on prevention modality on an ongoing basis: oral PrEP, or oral PEP, and the option to switch between products. The trials are being conducted in 3 settings: antenatal (ANC) clinics, the outpatient department (primary care clinics), and in rural community settings in Western Uganda and Kenya. All clinic and village health team staff (i.e., Clinical Officers, nurses, coordinators, health workers) are trained and equipped for HIV prevention care in the clinical setting, appropriate to their role.

In this extension study, participants in the intervention and control arms are reconsented and remain in their initial randomized arm. Persons in the intervention arms who remain HIV negative will be offered CAB-LA as an additional biomedical prevention option, if eligible. CAB-LA will be delivered at health clinics. The primary 48-week endpoint for this extension is proportion of time covered by a biomedical prevention product. As of May 9, 2022, a total of 1213 HIV-negative persons aged 15 years and older and at risk for HIV acquisition were enrolled in the studies. (Table 1). New participants are currently being enrolled in the original SEARCH SAPPHIRE DCP trials to replace those participants who have moved or have been unable to continue in the DCP study. The total number of participants in the study eligible for CAB-LA will not exceed the 593 listed in Table 1.

Table 1. Enrollment in 3 SEARCH Sapphire Dynamic Prevention Trials as of May 9, 2022

Dynamic Prevention Study	Intervention and Control, (N) Uganda	Intervention (N) Uganda	Intervention and Control, (N) Kenya	Intervention (N) Kenya	Total Enrolled (N), Intervention and Control	Total Enrolled Intervention (N)
Antenatal/SRH Clinic	200	100	201	103	401	203
Outpatient Department Clinics	201	100	201	97	402	197
Household Study Community Village Health Team (VHT)	200	83	210	110	410	193
All Trials Together	601	283	612	310	1213	593

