9. INFORMED CONSENT

9.1 Informed Consent Process

All participants in the DCP trials will be offered participation in the CAB-LA Extension. Consent forms will be translated from the original English to the language(s) spoken in the community. The consent form will be read to participants in their local language. Participants who agree to take part and sign the consent form will continue in the study. In this consent, women will be informed about the risks and benefits of CAB-LA during pregnancy and breastfeeding. In the case that participants become pregnant while using CAB-LA, they will be asked for an additional re-consent to follow-up for ascertainment of pregnancy and infant outcomes.

Participants will remain in the randomization arm they were assigned to at their initial DCP visit in Phase A. Participants in the SOC arm will consent to return for two additional follow-up visits at weeks 24 and 48 following re-consent for the CAB-LA extension. Intervention participants that do not choose CAB-LA will consent to continue the quarterly study visits and Intervention participants that choose CAB-LA will have study visits that align with their injection visits (every 4 weeks for the first two months and then every 8-weeks thereafter). Intervention participants will have flexibility to switch between PrEP, PEP, and CAB-LA. Unlimited switches between biomedical prevention options, including between CAB-LA and oral, will continue to be permitted during the extension, both to reflect participant choice and to bridge planned missed doses of CAB-LA. Clients and providers will discuss options for prevention and risk during regular visits and interim visits, in addition to continuous provider trainings on offering choice and refreshers for clients. Changes in prevention choices will be documented in study eCRF forms, which will include the CAB-LA option. DCP intervention participants that choose the CAB-LA option will be informed about the visit schedule, side effects, and risks and benefits, before consenting. If CAB-LA becomes available via the Ministry of Health during the trial, persons in the control arm will be eligible as per standard of care.

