3. ENDPOINT DEFINITION AND MEASUREMENT

3.1. Biomedical HIV Prevention Coverage

The primary endpoint of this study is biomedical HIV prevention coverage, defined as the proportion of follow-up time covered by either PrEP (TDF/3TC or CAB-LA) or PEP. Thereby, this endpoint has a minimum of 0% (no use) and a maximum of 100% (full coverage). For oral PrEP and PEP, coverage is defined using self-report via a structured survey administered at 24 and 48 weeks of follow-up. Specifically, for each month of the prior 6 months, participants retrospectively report any use of oral PrEP (i.e., pill ingestion) and any use of PEP. For CAB-LA, coverage is defined through injection logs. Coverage from CAB-LA begins 3 days after an injection and continues for 67 days.

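### Table 4 makes offering CAB-LA part of Adoption, but the only source it names for offers is a log of product given

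*Protocol*

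**What the plan says.** Protocol Section 7.3.2, Table 4, defines Adoption as the percentage "of staff and providers invited that participate in the interventions". It then gives this measure two components: "participation is defined as i) participation in CAB-LA trainings; and ii) offering CAB-LA to participants". The level is provider and staff in different settings, and the table adds a comparison of the characteristics of participating and non-participating staff. The measurement column reads: "Training attendance rosters; CAB-LA dispensing logs".

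The same logs appear elsewhere in Table 4. They serve Reach ("Proportion of eligible participants who initiate CAB-LA weeks 0-48"), Effectiveness, Fidelity and Maintenance (persistence on CAB-LA). SAP Section 3.1 uses a comparable record: "For CAB-LA, coverage is defined through injection logs".

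On where CAB-LA is given and by whom:
- Section 4.1 states "CAB-LA will be delivered at health clinics".
- Section 10.2 restricts administration to trained healthcare staff.
- Section 5.2 has the nearest health facility offer CAB-LA for the VHT/CHV communities.
- Section 7.3.1 distinguishes providers who administer CAB-LA from VHTs and CHVs "who inform the community about that option".

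On other records: Table 5 schedules an offer of prevention options at baseline and Weeks 12, 24 and 36 for intervention participants not receiving CAB-LA. Section 9.1 says "Changes in prevention choices will be documented in study eCRF forms, which will include the CAB-LA option". Neither is named as a source for Adoption.

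**The concern.** An offer and an injection are different events. The first is something the provider does. The second also needs the client to accept and to meet the CAB-LA eligibility criteria. If a log of product given stands in for offers, a provider can do what the definition asks and leave no trace.

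Three kinds of offer would be lost:
- offers that the client declines in favour of oral PrEP, PEP or nothing;
- offers to clients who then fail the additional CAB-LA criteria in Section 5.2, such as pregnancy at first injection, hepatitis B or raised ALT;
- offers or referrals by staff who do not inject, which includes VHTs and CHVs if they are among the invited staff.

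The first two understate offering in every setting. Pregnancy exclusions could bear most on antenatal staff. The third could lower the community figure because of where injections are given, not because of what staff do. The comparison of participating and non-participating staff would carry the same misclassification.

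**Working it through.** The documents give no target, expected rate or sample size for Adoption, so there is no plan figure to reproduce. The check sets definition against source and then sizes the loss under stated assumptions.

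**Step 1. Match components to sources.**
- Component (i), training participation: attendance rosters record it directly.
- Component (ii), offering: rosters cannot show it. The only other named source is the dispensing log.
- In the Reach and Maintenance rows, that log is the evidence that CAB-LA was received. No record of offers or refusals is named for Adoption.

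The mismatch is therefore in the table itself. It does not depend on any figure.

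**Step 2. Declined offers.** Suppose a provider offers CAB-LA to n clients, each accepting independently with probability p. The chance of no log entry is (1 − p)^n. The documents give neither n nor p, so both are assumed.

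| Uptake p | n = 5 | n = 10 |
|---|---|---|
| 10% | 0.59 | 0.35 |
| 20% | 0.33 | 0.11 |
| 30% | 0.17 | 0.03 |
| 50% | 0.03 | 0.001 |

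With 25 clients at 20% uptake, 0.8^25 = 0.004, or 0.4%.

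As a rough guide to n, Table 1 gives 593 intervention participants, and Section 5.2 has 11 site listings (5 in Uganda, 6 in Kenya). That is 593/11 ≈ 54 participants per listing. If clients do not overlap between providers, n = 5 implies about 54/5 ≈ 11 providers per listing, and n = 25 implies about 2. Provider numbers are not stated.

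**Step 3. Non-injecting staff.** If a share s of the denominator never injects, component (ii) scored from the log cannot exceed 1 − s, even when everyone offers CAB-LA. The only staff mix in the documents is the provider interview sample in Section 7.3.1: 2–3 OPD, 2–3 ANC/PNC and 1–2 VHTs per region.
- Smallest VHT share: 1/(1 + 3 + 3) = 14%, so the ceiling is 86%.
- Largest VHT share: 2/(2 + 2 + 2) = 33%, so the ceiling is 67%.

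This is a weak proxy. It describes interviewees rather than invited staff, and its parts add to 5–8 while the same item gives a total between 8 and 12 per region. It shows the form of the loss more reliably than its size.

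**The case against.** The strongest reply is that the consequence is not established. Adoption also has a training component, which the rosters cover, so a trained VHT or a trained provider with no acceptors still counts there if the components are reported separately. The documents do not give the log's fields, the scoring rule, or the cadres in the denominator. Dispensing and accountability procedures sit in pharmacy SOPs (Section 10.3), and SAP Section 1 says that plans for implementation metrics are held elsewhere. All of this stands, and the point is conditional for that reason. It does not supply a source for offers in Table 4.

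A reader might infer that community staff are recorded as non-adopters by design. The documents do not support that. Section 5.2 assigns the offer in those communities to the nearest facility, whose staff would have log entries, and nothing states that VHTs and CHVs are in the denominator. Table 3 does direct education to health centre leadership and staff, and Section 4.1 counts village health team staff among those trained for HIV prevention care, so inclusion is plausible and needs settling.

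A reader might also infer that Adoption merely repeats Reach. It does not: Reach is a proportion of participants, Adoption is a proportion of staff, and a single acceptor is enough to register a provider. As contacts accumulate, log-based offering approaches 100% among injecting staff whatever the uptake.

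Nor does the Fidelity row clearly share the fault. Its wording can be read as injection timing and oral bridging, which dispensing logs do capture.

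Finally, a log is more objective than a provider's report that an offer was made. That is a real trade-off, but an objective record of a different event does not measure offering.

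**Conclusion.** The point holds as a mismatch between a definition and its named source. If component (ii) is scored from dispensing logs as Table 4 stands, offering is understated, and the setting and staff comparisons can be distorted.

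The size depends on unstated inputs. Loss from declined offers is material for providers with few clients or low uptake (33% with no entry at 5 clients and 20% uptake) and negligible at higher volume (0.4% at 25 clients). Loss for staff who do not inject is systematic, but arises only if they are in the denominator; the 67% to 86% ceiling rests on the interview mix as a proxy.

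The reach of the problem is limited. Section 21.1 analyses Adoption by descriptive statistics, with no test. The primary endpoint, its significance level and its power are unaffected. The change is still worth making, because RE-AIM evaluation is the declared secondary objective and the remedy is cheap.

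**What to change.** In Table 4:

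1. Measure component (ii) from an offer/decline field (CAB-LA offered, yes or no, with staff ID), completed at the visits where Table 5 already schedules the offer of prevention options. Section 9.1 shows that the eCRF captures changes in choice; it does not show that it captures offers. Add the field if it is missing.
2. Report components (i) and (ii) separately.
3. State the denominator by cadre. For VHTs and CHVs, either count informing or referral as their form of offer, or exclude them from component (ii).
4. Keep dispensing logs for Reach, for injection timing and bridging under Fidelity, for persistence, and as a cross-check on reported offers.

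The cost is a wording change in Table 4 and at most one yes/no field with staff ID on an existing form. The downside is that the offer is reported by the provider; the cross-check against the logs limits this only in part, since it cannot verify a declined offer.
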